### **Methodology:**

Recruit 30 willing patients with peripheral vascular disease and claudication at the vascular surgery clinic at the Nebraska and Western Iowa Veterans Affairs Medical Center (VANWIHCS) in Omaha. 10 patients will be recruited from the total 30 patients for the intervention phase and rest of the 20 patients will only participate in the baseline phase. Patients will be evaluated by a Board-Certified Vascular Surgeon to determine if they have PAD and whether they are eligible to participate in the study the study. Subject will be consented prior to the study.

#### **1. Inclusion/Exclusion Criteria**

**Inclusion criteria:** At entry into the study, all subjects must:

- a. Be able to provide written, informed consent
- b. Demonstrate positive history of chronic claudication
- c. Demonstrate exercise-limiting claudication established by history and direct observation during a screening walking test administered by the evaluating vascular surgeon
- d. Have an ankle/brachial index  $<0.90$  at rest
- e. Have a stable blood pressure regimen, stable lipid regimen, stable diabetes regimen, and risk factor control for 6 weeks

**Exclusion criteria:** Any potential subjects will be excluded if they have:

- a. Rest pain or tissue loss due to PAD (Fontaine stage III and IV)
- b. Acute lower extremity ischemic event secondary to thromboembolic disease or acute trauma
- c. Walking capacity limited by conditions other than claudication, including leg and systemic pathology

#### **2. Patients will perform Gardner protocol on the pressure treadmill at the VA at Omaha, NE.**

- a. Normal walking shoes

- b. Carbon fiber insole shoes
  - c. Spring loaded shoes
- 3. Clinical data to be collected
  - a. ABI
  - b. Medical conditions/comorbidities
- 4. Voluntary Data Repository- If the patient agreed a study and health data will be de-identified and store in a special VA research drive only available to authorized research personnel. Information will be used for future studies about PAD or other vascular diseases. If the patient agrees he will be asked to sign a special HIPPA form.

**Statistical Analysis:** The sample size was calculated to detect effect sizes observed in pilot data for ankle plantarflexor push off. A sample size of 30 subjects will provide 79% power to detect differences of 0.30 standard deviations between walking with control and assistive tennis shoes, using a paired t-test for sample size estimation purposes only, and a significance level of 0.02 to informally adjust for multiple testing. For statistical analysis, a linear (or generalized linear, as appropriate) mixed modeling approach will be used. This approach will allow us to detect differences between walking with and without an AFO while adjusting for confounding variables. The level of significance will be set at 0.05.

Descriptive statistics will be used to summarize results of survey data. We will use counts and percents for categorical data and means and standard deviations for quantitative data. Associations between walking performance and comfort, fatigue, perceived intensity, and feasibility variables will be examined using t-tests for dichotomous variables and correlations for continuous variables. Comparisons will be done independently for each shoe type.

We expect differences from a 3-month intervention to be larger than the immediate differences shown in Aim 1. A sample size of 30 subjects would provide 80% power to detect differences of 0.59 standard deviations between walking with and without assistive tennis shoes, using a paired t-test for sample size estimation purposes only, and a significance level of 0.025 to adjust for multiple testing. For this pilot study, we plan to collect 10 subjects after the intervention and seek additional funding to fully power the study.

For statistical analysis, a linear mixed modeling approach (or generalized linear mixed model, as appropriate) will be used. This approach will allow us to detect differences within and between groups (different types of assistive shoes), and adjust for confounding variables. The main comparison of interest will be changes in walking distances due to wearing the assistive shoes. This pilot study will allow us to detect if walking distances improve after wearing the assistive shoes for 3-months. To evaluate the relationship between improvements in walking performance, physical activity, and quality of life, multiple correlations will be used. The level of significance will be set at  $p=0.05$ .

Outcome measure	Mean 1	Mean 2	Difference	Standard Deviation	Power	Required Sample Size
Push-off 	1.4	1.7	-0.3	0.30	0.79	29
Visual analog scale 	5.0	7.0	-2.0	2.00	0.81	30
Borg (scenario 2) 	14.0	11.0	3.0	2.50	0.81	23

Assumptions for sample size calculations to obtain 80% power. The test statistic is a two-sided paired t-test with an assumed correlation between mean 1 and mean 2 of 0.30. The alpha level is assumed as 0.001 to account for multiple comparisons between the different shoe types. Mean 1 is assumed as normal walking the control shoe and mean 2 is walking in the best assistive shoe. Choosing the largest sample size across all measures will ensure the desired power for all outcome measures\*.

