- 1) **Initial and maximum claudication distance on our instrumented treadmill using the Gardner protocol:** Subjects will complete a Gardner treadmill walking. Subjects will walk in a dynamic gait and pressure analysis treadmill (FDMT Scifit AC500M, Noraxon USA, Inc., Scottsdale Ariz) located at the VA Medical center at Omaha. This treadmill collects synchronized pressure measurements allowing for gait analysis and the calculation of steps taken during exercise. Participants initiated exercise at 2.0 miles per hour at 0.0% incline. With each subsequent 2-minute stage, the treadmill incline was increased 2.0% to a maximum of 12.0%. Time of initial symptoms (claudication onset time [COT] and time at which claudication symptoms were prohibitive to further walking [peak walking time] will be recorded. Data will be collected using regular shoes and specially designed (carbon fiber insole shoes and spring) shoes. They will be allowed to rest for 15 minutes between tests. Patients will do 3 walks in the treadmill (regular walking shoes, carbon fiber insole shoes, and spring shoes).

2) **Calf muscle saturation at one-minute walking:** Bilateral gastrocnemius muscle oxygenation (StO2) will be measured using continuous-wave near infrared spectroscopy (PortaMon, Artinis Medical System, Netherlands) before, during and after each treadmill walking condition (described above). Measurements will be continuously captured during the exercise and recovery interval. We will measure resting StO2 and StO2 at 1-minute walking.

3) **Vertical ground reaction forces in the first two minutes of walking:** Biomechanical data will be collected with a dynamic gait and pressure analysis treadmill (FDMT SciFit AC5000M, Noraxon USA, Inc.). The parameter measured will be the vertical ground reaction force.

4) We will use the Borg Rating of Perceived Exertion (RPE) questionnaire after each condition

5) **Physical Activity:** Participants will wear the Actigraph (Actigraph GT3X, Actigraph, FL, USA) accelerometer on their hip for seven days (the whole day except when sleeping) prior to starting the intervention phase to measure baseline activity level and seven days after the intervention phase to measure post-intervention physical activity. Average steps/day, maximum cadence, and average peak activity index will be calculated.

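### The acute-phase power statement (30 subjects, 0.30 SD, alpha 0.02, 79%) does not follow from its own inputs, which give about 22%

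*Combined protocol and SAP*

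**What the plan says.** Statistical Analysis, first paragraph, gives the basis of the acute-phase sample size: "The sample size was calculated to detect effect sizes observed in pilot data for ankle plantarflexor push off". It then states: "A sample size of 30 subjects will provide 79% power to detect differences of 0.30 standard deviations", "using a paired t-test for sample size estimation purposes only, and a significance level of 0.02 to informally adjust for multiple testing". The analysis itself is a mixed model, and for it the paragraph says: "The level of significance will be set at 0.05".

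The third paragraph makes a statement of the same form for the 3-month phase: "A sample size of 30 subjects would provide 80% power to detect differences of 0.59 standard deviations", again with a paired t-test, at alpha 0.025.

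A sample-size table closes the section. Its push-off row has means 1.4 and 1.7, difference -0.3, SD 0.30, power 0.79 and required n 29. Its note says: "The test statistic is a two-sided paired t-test with an assumed correlation between mean 1 and mean 2 of 0.30", and "The alpha level is assumed as 0.001 to account for multiple comparisons between the different shoe types". The table has rows for push-off, a visual analog scale and Borg only.

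**The concern.** The two power sentences use the same number of subjects, the same test and nearly the same alpha and power. Yet one claims to detect an effect half the size of the other (0.30 against 0.59 SD). At least one of them looks wrong.

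The acute sentence is the plan's only general statement, in SD units, of what the acute comparison can detect. The table has no row for muscle oxygen saturation, ground reaction force or the first listed endpoint, "Initial and maximum claudication distance on our instrumented treadmill using the Gardner protocol". A reader with a null acute result on one of these could take it as excluding a 0.30 SD effect with 79% power. If the true power is far lower, that inference fails.

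**Working it through.** **Inputs.** Acute sentence: n = 30, effect 0.30 SD, paired t-test, alpha 0.02, power 79%. 3-month sentence: n = 30, 0.59 SD, paired t-test, alpha 0.025, power 80%. Table note: two-sided, correlation r = 0.30, alpha 0.001. Neither power sentence states sidedness, correlation or which SD is meant, so each reading is tried.

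**Formula.** Power = P(|T| > t_crit), where T is noncentral t with n − 1 degrees of freedom and noncentrality dz × √n. Here dz is the mean difference divided by the SD of the paired differences. If the effect d is in per-condition SDs, dz = d / √(2(1 − r)).

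**Step 1: try to reproduce 79%.** With dz = 0.30, the noncentrality is 0.30 × √30 = 1.643. The two-sided critical value at alpha 0.02 with 29 df is 2.462.

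| Reading of 0.30 SD (n = 30) | dz | Alpha | Power |
|---|---|---|---|
| SD of differences, two-sided | 0.300 | 0.02 | 22.4% |
| SD of differences, one-sided | 0.300 | 0.02 | 31.9% |
| Per-condition SD, r = 0.30, two-sided | 0.30/√1.4 = 0.254 | 0.02 | 15.8% |
| Per-condition SD, r = 0.30, one-sided | 0.254 | 0.02 | 23.7% |
| SD of differences, two-sided, analysis level | 0.300 | 0.05 | 35.5% |

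Simulation agrees: 0.225 for the first row, 0.159 for the third and 0.357 for the last.

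**Step 2: what does 79% correspond to?** Solving for dz at n = 30, two-sided alpha 0.02 and power 0.79 gives 0.600. In per-condition SDs with r = 0.30 that is 0.600 × √1.4 = 0.71.

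**Step 3: check the 3-month sentence.** With dz = 0.59, the noncentrality is 0.59 × √30 = 3.232. The critical value at two-sided alpha 0.025 is 2.364, and power is 80.2%. The sentence reproduces. This points to a two-sided test and the SD of differences, but does not prove it: a per-condition SD with r = 0.5 makes 2(1 − r) = 1 and gives the same figure.

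**Step 4: compare the two sentences under one convention.** The detectable dz is 0.600 (acute: alpha 0.02, 79%) and 0.589 (3-month: alpha 0.025, 80%) two-sided, a ratio of 1.02. One-sided they are 0.542 and 0.529, also 1.02. A correlation common to both sentences cancels from the ratio. The stated ratio is 0.30/0.59 = 0.51.

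**Step 5: the push-off row as a possible source.** The difference of 0.3 with SD 0.30 is 1.0 per-condition SD, so dz = 1/√1.4 = 0.845. At n = 29 and alpha 0.001 power is 79.3%, so the row reproduces. At n = 30 the same effect has 81.7% power at alpha 0.001 and 98.1% at alpha 0.02. The figures 0.30 and 79% appear in this row, but there 0.3 is a raw difference and alpha is 0.001.

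**Scale only.** At alpha 0.02, 79% power for 0.30 SD would take 112 subjects (two-sided, SD of differences), 94 (one-sided) or 156 (per-condition SD, r = 0.30, two-sided).

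**The case against.** The strongest defence is that 0.30 is a per-condition SD and that the pilot data showed a high correlation between shoes worn in the same session. With r about 0.875, 2(1 − r) = 0.25, dz = 0.30/0.5 = 0.60, and power is 79%. Walks separated by 15-minute rests may well correlate more strongly than measurements three months apart. With r = 0.875 for the acute sentence and r = 0.5 for the 3-month one, both would reproduce. This is arithmetically sound, and it limits step 4 to the case where both sentences share one convention. But no such correlation is stated. The only one printed is 0.30, for the control shoe against the best assistive shoe. Applied to the 3-month sentence as well, 0.875 would give more than 99.9% instead of 80%. As printed, the sentence still fails.

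It can also be said that no passage mentions a one-sided test. That is fair: the two-sided readings at alpha 0.02 run only from 15.8% to 22.4%, and the 31.9% is the more generous case.

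Finally, n = 30 does not depend on this sentence. The table's largest requirement is 30, from the visual analog scale row, and the t-test serves planning only. This stands, and it is why the remedy leaves the sample size alone. It does not make the printed power right.

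**Conclusion.** The concern holds. The stated 79% is not the power for the stated effect, sample size, test and alpha. The figure is 22.4% (two-sided, SD of differences), within 15.8% to 31.9% over the four readings at alpha 0.02, and 35.5% two-sided at the 0.05 analysis level. At face value the sentence says a true 0.30 SD effect would be missed 21% of the time. The planning test would miss it about 78% of the time at alpha 0.02 and about 64% at 0.05.

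That 79% is wrong for the printed inputs is certain on every one of these readings. What the authors intended is not. If 0.30 stands for 0.60, the true detectable effect is twice the stated one. If it is the raw push-off difference, the units are wrong, and 79% still does not belong with alpha 0.02. Either way, a null acute result on claudication distance, oxygen saturation or ground reaction force should not be read as excluding 0.30 SD with 79% power.

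**What to change.** Keep the sample size and restate the acute sentence, naming the SD and the alpha. Use whichever version matches the authors' intention:

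- **(A) If 0.60 SD was meant:** 30 subjects give about 79% power for a control-versus-assistive difference of 0.60 SD of the within-patient differences (two-sided paired t-test, alpha 0.02). Power for 0.30 SD of the differences is about 22% at alpha 0.02 and 36% at 0.05.
- **(B) If the table's push-off effect was meant:** 30 subjects give about 98% power at alpha 0.02 (82% at alpha 0.001) for a push-off difference of 0.3 units, which is 1.0 per-condition SD with correlation 0.30. Power for 0.30 SD of the differences is about 22% at alpha 0.02 and 36% at 0.05.

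The figures in the 3-month sentence and the push-off row reproduce and need no change.

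The cost is protocol wording only. Under (A) the stated sensitivity becomes less favourable, 0.60 SD instead of 0.30 SD. No patients are added and the design does not change.

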**Improving Walking in Peripheral Artery Disease**  
**ClinicalTrials.gov Identifier (NCT Number): NCT05103280**

## VA Tennis Shoes Protocol

**Title:** Improving Walking in Peripheral Artery Disease, Using Specially Designed Assistive Shoes

**Objective:** The objective of this research is to evaluate the ability of different **specially designed tennis shoes** to improve walking performance, muscle oxygenation of patients with peripheral artery disease (PAD).

**Hypothesis:** We hypothesize that the specially designed tennis shoes will provide assistance to the ischemic legs of patients with PAD and will therefore reduce the biological contribution and oxygen requirements of the ischemic leg muscles. This will acutely increase the walking performance, muscle oxygenation in the patients.

If our hypothesis is correct, the carbon fiber insole shoes and spring shoes may become a new effective conservative intervention for patients with PAD. However, if none of the components of our hypothesis are correct, then our study would direct us away from the carbon fiber insole shoes and/or spring shoes and toward other therapies.

We also hypothesize that an intervention with specially designed tennis shoes (spring loaded or carbon fiber insole shoes) will increase physical activity, and improve walking performance and quality of life. Our preliminary results show promising results in increasing the walking distances including initial claudication distances and absolute claudication distances during first-time use of the specially designed tennis shoes. Subjects will complete a 3month intervention with their preferred specially designed tennis shoe based on the initial data collection. They will be tested prior to starting the intervention and after 3 months of the intervention.

**Endpoints measured:** The patients will walk while wearing their own walking shoes, the carbon fiber insole shoes and the spring-loaded shoes (in random order) and we will measure the following performance endpoints for both phases:

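### The acute-phase power claim (79% for 0.30 SD at alpha 0.02, n = 30) recomputes to about 22%, and the analysis level of 0.05 is not tied to the adjusted alphas used for sizing

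*Combined protocol and SAP*

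**What the plan says.** All of this is in the protocol's Statistical Analysis section unless noted.

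- **First paragraph (acute comparison).** Sizing rests on pilot push-off data. Thirty patients are said to give 79% power for 0.30 SD between control and assistive shoes, "using a paired t-test for sample size estimation purposes only, and a significance level of 0.02 to informally adjust for multiple testing". The sentence states neither sidedness nor which standard deviation is meant. The planned analysis is a mixed model contrasting walking with and without an AFO, and then: "The level of significance will be set at 0.05".
- **Third paragraph (3-month phase).** Thirty patients are said to give 80% power for 0.59 SD with "a significance level of 0.025 to adjust for multiple testing". Only 10 patients are planned after the intervention.
- **3-month model paragraph.** The model is meant to detect "differences within and between groups (different types of assistive shoes), and adjust for confounding variables". It adds: "The main comparison of interest will be changes in walking distances due to wearing the assistive shoes". The level is again 0.05.
- **Sample-size table and note.** The push-off row has a difference of 0.3, SD 0.30, power 0.79 and n = 29. The largest required n is 30. The note specifies a two-sided paired t-test, a correlation of 0.30, and this: "The alpha level is assumed as 0.001 to account for multiple comparisons between the different shoe types".

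Item 1 of the endpoint list gives both initial and maximum claudication distance. Neither is named as primary for the acute comparison.

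**The concern.** The two power sentences use the same n and the same test. The acute one has the stricter alpha, yet claims about the same power for half the effect (0.30 against 0.59 SD). In the same units, both cannot be true. A reader who trusts the acute sentence would believe that 30 patients can detect an effect half the size they actually can, and might read a null result as evidence against a modest benefit.

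The second issue is which level governs the shoe contrasts. The sponsor recognised multiplicity three times when sizing, but the analysis paragraphs give 0.05 with no adjustment method and no overall test as a gate. The Hypothesis section says the study would "direct us away from the carbon fiber insole shoes and/or spring shoes and toward other therapies" only if no component of the hypothesis held. A positive result for either shoe would therefore be read as support, and the chance of at least one false positive depends on a rule that is not written down.

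**Working it through.** **Power.** For a paired t-test, df = n − 1 and the noncentrality is d√n, where d is the difference divided by the SD of the paired differences. If the effect is in raw SD units, d = effect / √(2(1 − r)).

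*The plan's figures that reproduce:*
- 0.59 SD, n = 30, alpha 0.025 two-sided: noncentrality 0.59 × √30 = 3.23; power 80.2% (stated 80%).
- Push-off row: d = 0.3 / (0.30 × √1.4) = 0.845; n = 29, alpha 0.001 two-sided; power 79.3% (stated 0.79).
- Visual analog scale row: d = 2.0 / (2.00 × √1.4) = 0.845; n = 30; power 81.7% (stated 0.81).
- Borg row: d = 3.0 / (2.50 × √1.4) = 1.014. The n of 23 reproduces; power is 83.4% (stated 0.81).

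*The figure that does not reproduce (stated 79%; n = 30, alpha 0.02):*

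| Reading of 0.30 SD | d | Power |
|---|---|---|
| SD of paired difference, two-sided | 0.30 | 22.4% |
| SD of paired difference, one-sided | 0.30 | 31.9% |
| Raw SD, table's r = 0.30, two-sided | 0.30/√1.4 = 0.254 | 15.8% |

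At alpha 0.05 two-sided with d = 0.30, power is still only 35.5%. With n = 30 and alpha 0.02 two-sided, 79% power corresponds to d = 0.60.

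**Is there one alpha rule?** 0.05/2 = 0.025 would fit an overall 0.05 over two shoes. But 0.05/0.02 = 2.5 and 0.05/0.001 = 50, so the other two sizing levels do not follow from that split.

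**Familywise error under the null.** These are simulations with n = 30, one distance, and carbon fiber and spring each against own shoes, two-sided. The correlation between the two contrasts is 0.5 if variances and correlations are equal across conditions. The values 0.75 and 0.875 are assumptions for two assistive shoes that behave more alike. Simulation error is about 0.1 percentage point.

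| Contrast correlation | 0.5 | 0.75 | 0.875 |
|---|---|---|---|
| Separate paired tests, 0.05 each | 9.1% | 8.2% | 7.4% |
| Separate paired tests, 0.025 each | 4.6% | 4.2% | 3.8% |
| Common error term, 0.05 each | 9.1% | 11.6% | 12.8% |
| Common error term, 0.05 each, only after overall F-test at 0.05 | 4.3% | 5.5% | 6.8% |
| Common error term, 0.025 each | 4.7% | 6.5% | 7.7% |

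The common-error rows rise because the pooled error averages the three pairwise difference variances. If each own-shoe contrast has variance 1 and their correlation is c, the average is (1 + 1 + 2(1 − c))/3. That is 1.00 at c = 0.5, 0.83 at 0.75 and 0.75 at 0.875, so the own-shoe contrasts are judged against too small an error.

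**The case against.** **The sample size does not depend on the faulty sentence.** This stands. The table's largest row gives n = 30 and reproduces. With the push-off effect in the table (d = 0.845), 30 patients would have 98% power at alpha 0.02. The sentence may be a units slip, with a raw push-off difference of 0.3 restated as 0.30 SD; that is inference. A reader might conclude that the trial is grossly underpowered or needs far more patients. The documents do not support that.

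**The sentence could be true on some reading.** It could be, if 0.30 is in raw SD units and the within-patient correlation is about 0.875, since √(2 × 0.125) = 0.5 and 0.30/0.5 = 0.60. The only correlation in the documents is 0.30.

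**0.05 may be the overall level.** It may. A reader might infer that the plan tests each shoe at 0.05; no sentence says so. Two passages come near the question without settling it. The remark that comparisons are made independently for each shoe type closes the survey-data paragraph and sets no level. The multiple-comparisons reference is attached to the sample-size table only.

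**The family of contrasts is not fixed.** The table note speaks of the best assistive shoe (one contrast), while the 3-month model paragraph mentions differences between types of assistive shoe (a further contrast). This is fair, and it is part of the same omission. If the best shoe is picked from the same data, the comparison is the larger of two and the question returns.

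**An overall F-test, or 0.025 each, would settle it.** Only conditionally. With a common error term both exceed 5% when the two assistive shoes behave alike.

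**Conclusion.** The acute-phase power sentence is wrong as written. On the documents' own inputs power is 16% to 32%, and 22% on the most natural reading (two-sided, SD of the paired difference). The difference detectable with 79% power is about 0.60 SD. The sentence also conflicts with the 0.59 SD sentence in the same section and with the push-off row, which reaches 79% from different inputs. Confidence in this part is high.

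The alpha point is real but smaller, and it is an omission rather than an error. The possible inflation (about 7% to 9% with separate paired tests, up to about 13% with a common error term) applies only if each of the two contrasts is tested at 0.05, and it depends on assumed correlations. The Hypothesis wording is not a formal go/no-go rule, so these rates measure the risk of an overstated claim, not of a wrong programme decision.

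The AFO wording names a device that is not among the three shoe conditions. It needs correcting but does not affect the error rate.

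**What to change.** 1. Restate the acute power sentence with sidedness and the SD defined, at the alpha actually used. For n = 30, two-sided, in SDs of the paired difference, this is about 0.60 SD at alpha 0.02 (79% power) or 0.59 SD at alpha 0.025 (80% power). Reconcile it with the push-off row. The section expects 3-month effects to exceed the acute ones, so say whether about 0.6 SD is plausible acutely. The documents give no variability for claudication distance.
2. For the 30-patient acute comparison, state that 0.05 is the overall level for carbon fiber versus own and spring versus own, on one claudication distance that the sponsor names as primary. Test at 0.025 each or by Holm.
3. Use paired differences or an unstructured within-patient covariance, so that each contrast has its own error and the level holds.
4. Treat carbon fiber versus spring and the other endpoints as secondary, with confidence intervals. Replace AFO with the two shoes.
5. Do not carry the two-contrast rule into the 3-month phase, where 10 patients each use one preferred shoe. Report estimates with confidence intervals there.

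**Cost.** Wording only, no added patients. If the contrasts would otherwise be tested at 0.05, the effect detectable with 80% power rises from 0.53 to 0.59 SD of the paired difference, and power at 0.50 SD falls from 75% to 65%. Keeping 0.53 SD at alpha 0.025 would take 37 patients.

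### The 3-month comparison between shoe types is a self-selected contrast in 10 patients and should be reported descriptively, not as an inference

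*Combined protocol and SAP*

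**What the plan says.** The Hypothesis section sets how the 3-month shoe is assigned: "Subjects will complete a 3month intervention with their preferred specially designed tennis shoe based on the initial data collection". Patients are measured before and after: "They will be tested prior to starting the intervention and after 3 months of the intervention".

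The only randomisation in the document is under Endpoints measured, and it concerns the order of the treadmill walks: patients walk in their own shoes, "the carbon fiber insole shoes and the spring-loaded shoes (in random order"). The same sentence says the performance endpoints apply to both phases.

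Methodology gives the size: "10 patients will be recruited from the total 30 patients for the intervention phase". The other 20 take part in the baseline phase only. No carbon-fiber/spring split is fixed for the 10.

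In Statistical Analysis, the fourth paragraph plans a mixed model for the 3-month phase that will "detect differences within and between groups (different types of assistive shoes), and adjust for confounding variables". The next sentence sets the priority: "The main comparison of interest will be changes in walking distances due to wearing the assistive shoes". The confounders are not named. The clinical data listed for collection are ABI and medical conditions or comorbidities.

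**The concern.** The groups in the planned between-group comparison are the shoe types worn for 3 months, and patients enter them by preference. The text does not say whether preference means the patient's liking or the better result at the initial testing. In either case the choice is tied to something that may also predict the 3-month change. If the better baseline walk decides, regression to the mean can enter the change scores as well.

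A carbon-fiber versus spring difference at 3 months could therefore arise with no difference between the shoes, or a real one could be hidden. The plan presents the comparison as something the model will detect after adjustment. It does not label it exploratory, descriptive or non-causal, so a reader of the results could take it as evidence that one shoe works better over 3 months.

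**Working it through.** **1. Design check (no arithmetic).** Three statements set side by side: the 3-month shoe is the preferred one (Hypothesis); randomisation covers walk order only (Endpoints measured); the 3-month model compares shoe types (Statistical Analysis, fourth paragraph). The shoe worn for 3 months is not randomised anywhere, so the contrast is observational.

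**2. What adjustment could do.** Walking distances, StO2, ground reaction forces and Borg ratings are recorded in each shoe at baseline, and ABI and comorbidities are collected. These could explain part of the choice. The reason for choosing a shoe is not a listed item, and the survey interview is placed at the end of the study. With 10 patients the model can carry very few covariates.

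**3. The plan's own power figure.** The third paragraph of Statistical Analysis states: "A sample size of 30 subjects would provide 80% power to detect differences of 0.59 standard deviations", by paired t-test at alpha 0.025. Noncentrality = 0.59 × √30 = 3.23 with 29 df. At two-sided 0.025 the power is 80.2%, so the figure reproduces. It refers to a paired contrast in 30 patients and does not cover shoe versus shoe. With n = 10 the same paired contrast has 26% power at alpha 0.025 and 39% at 0.05.

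**4. Precision of the shoe-versus-shoe contrast.** Assumptions: two-sample t-test on change scores, two-sided alpha 0.05, n₁ + n₂ = 10, 8 df, and effects in SD of change. The 0.59 SD is borrowed from the plan for illustration only.

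Noncentrality = d / √(1/n₁ + 1/n₂). Power of 80% needs a noncentrality of about 3.2, so the detectable difference is about 3.2 × √(1/n₁ + 1/n₂).

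| Split | √(1/n₁ + 1/n₂) | Difference for 80% power | Power at 0.59 SD |
|---|---|---|---|
| 5:5 | 0.632 | 2.02 SD | 13.1% |
| 6:4 | 0.645 | 2.07 SD | 12.8% |
| 7:3 | 0.690 | 2.21 SD | 11.8% |
| 8:2 | 0.791 | 2.53 SD | 10.1% |
| 9:1 | 1.054 | 3.37 SD | 7.9% |
| 10:0 | undefined | cannot be estimated | not applicable |

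If each patient were equally likely to choose either shoe (an assumption), the chance of a 7:3 or more uneven split is 2 × (120 + 45 + 10 + 1) / 1024 = 352 / 1024 = 34%.

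**5. Illustration of the bias.** The figures in step 4 measure imprecision, not bias. The bias cannot be computed from the documents, so a simulation was run on assumed inputs: no true shoe effect, and one unmeasured factor that explains 30% of the variance of change and drives choice with a log-odds of 1 to 2 per SD.

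- With 10 patients, the expected spurious difference is about 0.43 to 0.66 SD, with a false-positive rate of about 9% to 15%.
- With 30 patients, the spurious difference is about 0.45 to 0.67 SD, with a false-positive rate of about 22% to 44%.

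Under these assumptions the bias does not shrink with a larger sample, and it is more often declared significant.

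**The case against.** The strongest reply is that this is a minor clause in a declared pilot. The sentence after the quoted one names change in walking distance as the main comparison. The Hypothesis section treats the two shoes jointly, with no shoe-versus-shoe hypothesis for the 3-month phase. The quoted words can be read as describing what a mixed model is able to do. The plan also admits that the phase is not fully powered: "we plan to collect 10 subjects after the intervention and seek additional funding to fully power the study". Labelling the contrast exploratory and naming the covariates might then be enough.

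Most of this stands as to weight: the contrast is secondary. It does not remove the problem. The clause says the approach will detect between-shoe differences, and it carries no exploratory label. Pilot status excuses low power but not self-selection, which more patients would not cure.

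A second reply is that, because the endpoints apply to both phases, all three shoes may be walked in again at 3 months, giving a within-patient shoe contrast. The text allows that reading. Even so, each patient would have had 3 months in only one assistive shoe, so the contrast would still be affected by which shoe was chosen.

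Three stronger readings are tempting, and the documents do not support them:

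- A reader might infer that no covariate could separate shoe from preference. That is too absolute, because baseline results in each shoe are measured and could account for part of the choice.
- A reader might infer that the contrast will steer a larger study to the wrong shoe. The document speaks only of seeking funding to power this study fully, and nowhere says that a 3-month contrast will select a shoe.
- A reader might infer that the whole 3-month analysis is confounded by shoe choice. The main comparison is change within patients, not a contrast between shoe groups.

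**Conclusion.** The concern holds for the between-shoe-type comparison in the 3-month phase and for nothing wider. As written, the plan would produce a self-selected contrast in 10 patients, with adjustment for unnamed variables that could remove only part of the bias. This rests on the text alone, where preference sets the shoe and no randomisation applies to it.

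The size of the bias is unknown, and the simulated values depend on assumed inputs. The imprecision can be stated: about 2.0 SD (5:5) to 3.4 SD (9:1) for 80% power, and 8% to 13% power at an illustrative 0.59 SD, under a two-sample t-test at two-sided 0.05.

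The main comparison is not subject to this problem. It has other limits, such as the absence of a concurrent control, which are separate matters.

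**What to change.** In the fourth paragraph of Statistical Analysis:

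- Remove the between-shoe-type comparison from the 3-month inference.
- Report 3-month change by worn shoe descriptively, with the number of patients in each shoe and a statement that the groups are self-selected.
- Take the carbon-fiber versus spring comparison from the random-order baseline walks in all 30 patients, and describe it as an acute comparison.
- State the 3-month question as within-patient change with the patient's preferred assistive shoe.

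The cost is wording only, with no change to procedures, visits or patient numbers. The sponsor gives up one secondary planned inference. The baseline walks do not replace it in full, because they show acute differences between shoes and not 3-month ones.
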